#### **14.3.2 Response**

Both overall response and response at un-irradiated sites will be determined at week 12, 3 months after completing the first cycle of pembrolizumab and SRS (i.e C1D2-3). Responses will be determined by the RECIST and immune RECIST criteria, as described in APPENDIX II and III. Response will also be assessed at 1 year from C1D2-3. Response rates will be reported along with 95% confidence intervals will be estimated using the Clopper-Pearson method.

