All patients will have a baseline PET scan as well as a diagnostic CT chest, abdomen, and pelvis. All pre-treatment and post treatment imaging will be per standard of care for staging and surveillance purposes. They will also have a baseline brain MRI. Post SRS treatment, they will continue to have diagnostic brain MRI (at 6 weeks, and then every 3 months) as well as CT chest/abdomen/pelvis (every 3 months) per standard of care, to evaluate response and to monitor for any unexpected toxicity. Routine standard of care blood work (CBC, BMP, LDH, etc) will also be ordered at baseline and with all subsequent visits.

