#### **3.2.3 Secondary Endpoint Definitions**

- a. Time to recurrence for each of the intracranial events will be measured from the first treatment on cycle 1, day 1 to the earlier of the recurrence event and/or last follow up/death.
- b. Overall survival will be defined as time from first treatment on cycle 1, day 1 to the earlier of date of death and/or last follow up.
- c. Overall response will be defined using RECIST and immune RECIST Criteria. Response will be measured for all metastatic sites and at un-irradiated sites (i.e. the abscopal effect).
- d. Several serum biomarkers will be analyzed (See section 12) to note any differences between the three arms.

- e. Symptomatic radiation necrosis is defined as evidence of necrosis on MRI images (radiographic evidence or radionecrosis) and a patient having neurological symptoms attributed to the location where the radiosurgery was done (symptomatic); Secondary Hypotheses

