#### **4.2.1 Efficacy of Anti-PD-1, Pembrolizumab, in Melanoma Patients**

Two clinical trials have recently investigated the safety and efficacy of anti-PD-1 pembrolizumab therapy in melanoma. The first published trial by Hamid et al enrolled 135 patients who had never received ipilimumab or had completed ipilimumab greater than 6 weeks

from enrollment. Patients were treated with escalating doses of pembrolizumab, from 2mg/kg q3weeks to 10mg/kg q2weeks. After 4 cycles of induction therapy, patients were continued on pembrolizumab maintenance. The overall response rate was 38% of patients. Response rate was also dose related, with 2mg/kg cohort having a 25% response compared to the 10mg/kg cohort having a 52% response. With a median follow up of 11 months, 81% of patients continued to demonstrate a response and median survival had not been reached, suggesting majority of responses are durable and correlate with survival.

The second reported by Robert et al was a phase I trial of pembrolizumab in metastatic melanoma patients. 173 patients refractory to ipilimumab were randomized in a 1:1 fashion to 2mg/kg q3weeks or 10mg/kg q3weeks. Overall response rate for both dose cohorts was similar: 26%. Of the 41 responding patients, 2 had a complete response (4.9%) while 39 had a partial response (95.1%). Another 24% had stable disease, for a disease control rate of 50%. Progression free survival was 22 weeks for the 2mg/kg arm and 14 weeks for the 10mg/kg arm, with no statistical difference between cohorts. 1 year overall survival was 58% for the 2mg/kg cohort and 63% for the 10mg/kg cohort.

Taken together (**Table 3**), these studies suggest pembrolizumab is an active agent in metastatic melanoma that is well tolerated. Based on these results, the FDA approved pembrolizumab for ipilimumab refractory patients, at a recommended dose of 2mg/kg every 3 weeks +/- 7 days.

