#### **4.4.1 Safety and Efficacy of Pembrolizumab Alone for Melanoma Brain Metastases**

For both published pembrolizumab trials (Hamid et al & Robert et al), patients with melanoma brain metastases were excluded. With melanoma having a high incidence of developing brain metastases, the efficacy in this population is extremely important. To investigate this further, Kluger et al (Yale group) conducted a phase I study of pembrolizumab alone for melanoma brain metastases. Only patients with asymptomatic lesions and ECOG PS 0-1 were included.

Patients were treated with 10mg/kg q2weeks for 4 total cycles, followed by maintenance therapy. All patients were asymptomatic and not requiring steroids (less than or equal to 10 mg prednisone equivalent is ok)s at the time of start of treatment. 18 patients were enrolled; however 4 (22%) were deemed not evaluable due to intralesional hemorrhage (n=1) and extracerebral progression (n=3). 4 patients (22%) developed a response, with 1 a complete response and 3 with partial responses. Another 3 patients developed stable disease. In the evaluable patients, 7 out of the 14 developed progressive disease (50%). Given the response rate (22%) is similar to the response rate seen in the extra-cranial metastases patients (Hamid et al.; Robert et al.), the authors concluded pembrolizumab does have similar intracranial efficacy.

However in comparison to the standard of care regimens such SRS alone, where 1 year LC rates in prospective studies are 67-75%, the LC rates with pembrolizumab appear significantly lower. With 11 out of the 18 patients (61%) either not completing treatment or developing progressive disease, these tolerability-efficacy rate is markedly lower for pembrolizumab for non-CNS metastases. One possible conclusion is that delayed immunologic response characteristic of pembrolizumab may not be quick enough in the brain, where relatively smaller amounts of progression can quickly increase neurologic morbidity and mortality. Another reason may be that pembrolizumab may not penetrate the blood brain barrier to enough concentrations to make a meaningful clinical impact. Thus, the combination approach of SRS for local control of disease within the brain and pembrolizumab for the control of extra-cranial systemic disease makes the most logical sense. The safety and efficacy of these two combination delivered concurrently is not well characterized.

[figure not shown]

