### 6.5 Administration of Pembrolizumab Beyond Progression

If the initial week 12 scan shows disease progression per RECIST 1.1, patients are allowed to continue treatment until progression is confirmed again at a subsequent 4-6 week later, to account for atypical response patterns. If the repeat imaging shows evidence of disease stabilization or objective response (relative to the previous scan that showed PD) as per RECIST 1.1, pembrolizumab may be continued per treatment calendar. However, if the repeat assessment shows disease progression relative to the previous scan that showed PD, then pembrolizumab should be discontinued; The minimum criteria to continue must include absence of symptoms/signs of disease progression, no decline in performance status, and absence of rapid progression of disease at critical anatomic sites (i.e cord compression) requiring urgent alternative medical intervention.

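### Response is reported only as two landmark rates, while the planned historical comparison is with overall response rates, so no like-for-like rate is named

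*Combined protocol and SAP*

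**What the plan says.** Section 14.3.2 fixes two reading dates: "Both overall response and response at un-irradiated sites will be determined at week 12", and "Response will also be assessed at 1 year from C1D2-3". On the analysis it says "Response rates will be reported along with 95% confidence intervals", by the Clopper-Pearson method. Section 3.2.3(c) adds only that "Overall response will be defined using RECIST and immune RECIST Criteria". Neither section mentions best overall response, confirmation of response, a rule for combining the two readings, or how patients who have died or have no evaluable scan enter the denominator.

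Objective c (section 3.2.1) sets the overall response rate against historical SRS alone and historical pembrolizumab alone. Hypothesis c (section 3.2.4) expects, descriptively, a higher response rate than with pembrolizumab alone. The pembrolizumab response rates given in section 4 include 38% and 26% in melanoma (4.2.1) and 19.4% in NSCLC (4.2.2).

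The protocol also expects response to be slow or irregular. Section 4.4.1 suggests that the "delayed immunologic response characteristic of pembrolizumab may not be quick enough in the brain", and section 6.5 allows treatment past progression on the week 12 scan "to account for atypical response patterns". Body imaging is more frequent than the two reading dates: section 2.1 plans "CT chest/abdomen/pelvis (every 3 months", under standard of care. Appendix III computes irRC tumour burden at every on-study assessment, and section 16.1 lists imaging with RECIST among the captured data.

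**The concern.** A landmark rate counts patients in response on a given date. An overall response rate, as usually reported, counts patients who responded at any time. The first cannot exceed the second in the same patients with the same denominator and confirmation rule, and it falls below it when some responses start late or end early.

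The protocol's own account of the first melanoma trial points to an ever-responded benchmark. It gives an overall response rate of 38% and then says: "With a median follow up of 11 months, 81% of patients continued to demonstrate a response". Because 81% exceeds 38%, it can only sensibly mean 81% of responders. The 38% then includes about 19% of responders who were no longer responding.

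If the plan is followed as written, the reader will have two landmark rates and a historical overall rate to set them against. A shortfall could come from the definition alone. A secondary objective of the trial would then rest on a comparison that is not like for like.

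**Working it through.** The plan gives no target rate, power or sample size for response, so there is no figure of its own to reproduce. Its single power statement (72%, section 14.1.2) concerns survival and has no bearing here.

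**Inputs**
- R, the true ever-responded rate: 38%, 26% or 19.4% (sections 4.2.1 and 4.2.2).
- K, the share of responders still in response at 1 year: 0.81 from section 4.2.1. It was reported at a median follow-up of 11 months, so it is a proxy.
- L, the share of responders who first respond after week 12: not in the documents; 0.1 to 0.4 is assumed.
- L and K are taken as independent, and all patients are in the denominator.

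**Formulas**
- Week 12 rate = R × (1 − L)
- 1-year rate = R × K
- Missed at both readings = R × L × (1 − K)

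**With R = 38%**
- Week 12: 0.38 × 0.9 = 34.2%, down to 0.38 × 0.6 = 22.8%. The shortfall is about 4 to 15 points.
- 1 year: 0.38 × 0.81 = 30.8%. The shortfall is about 7 points.
- Missed at both: 0.38 × 0.1 × 0.19 = 0.7 points, up to 0.38 × 0.4 × 0.19 = 2.9 points. That is 0.1 to 0.3 patients of 12, or 0.2 to 0.9 of 30.

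| True rate | Week 12 (L 0.1 to 0.4) | 1 year (K 0.81) | Missed at both |
|---|---|---|---|
| 38% | 34.2% to 22.8% | 30.8% | 0.7 to 2.9 points |
| 26% | 23.4% to 15.6% | 21.1% | 0.5 to 2.0 points |
| 19.4% | 17.5% to 11.6% | 15.7% | 0.4 to 1.5 points |

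**Sensitivity to durability.** With K = 0.5 (an assumption) and R = 38%, the 1-year rate is 19.0% and 1.9 to 7.6 points are missed at both.

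**Sensitivity to the denominator.** If only patients alive at 1 year were counted, and 78% were alive (the survival figure in section 14.1.2, used only as an illustration), 30.8% would become 0.308 / 0.78 = 39.5%. The unstated denominator alone can therefore hide or reverse the 1-year shortfall.

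**Sampling error.** The Clopper-Pearson 95% interval is 15% to 72% for 5 of 12, and 20% to 56% for 11 of 30.

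**The case against.** The strongest defence is that the two readings cover most responders between them. A patient who responds by week 12 and relapses is counted at week 12. A late responder still in response at 1 year is counted then. This stands, and it limits the combined loss to about 1 to 3 points at 81% durability. However, the plan reports the two rates separately and has no rule for combining them, so the single-landmark shortfalls are what a reader would meet.

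It also stands that the comparison is descriptive, that no error rate or power depends on it, and that sampling error exceeds the shortfall. The documents do not define the historical rates outright. If those required confirmation and the trial's landmarks do not, the gap would be smaller or could vanish. Fixed landmarks are a legitimate endpoint and depend less on scan frequency. Intermediate scans are assessed and recorded, so the gap is in the named rate and not in the data.

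Three stronger readings are tempting, and the documents do not support them:
- **That the choice of arm is biased.** Sections 2.3 and 14.1.2 use systemic response in choosing the arm, but all arms share the same landmarks and no differential effect is shown.
- **That section 6.5 turns responders into non-responders.** The repeat scan there is judged against the scan that showed progression, as a rule for continuing treatment. Improvement from that scan need not be a response from baseline.
- **That the flow chart contradicts week 12.** Cycles 4 and 5 run from day 64 to about day 105, which includes both day 84 (week 12) and about day 93 (3 months after C1D2-3). The window is loose but consistent.

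**Conclusion.** The point holds as a mismatch between the rates planned and the comparison intended. Each landmark alone would understate a true 38%: to about 31% at 1 year, and to about 34% to 23% at week 12. The 1-year figure rests on 81% serving as a 1-year proxy and on all patients being in the denominator. The week 12 figure rests on the assumed 10% to 40% late-response share. Reading the historical rates as ever-responded is well supported for the first melanoma trial and inferred for the others.

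A reader might infer that late responders, and responders who relapse before 1 year, are lost altogether. They are not: only patients who both respond late and lose the response before 1 year escape both readings. With a descriptive secondary comparison and intervals this wide, the change is a modest and inexpensive improvement. It does not put the trial's main conclusions in question.

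**What to change.** In sections 3.2.3(c) and 14.3.2:
- Name best overall response, by RECIST 1.1 and separately by irRC, over all scheduled scans from baseline to 12 months, as the rate set against historical overall response rates.
- Report it for all sites and for un-irradiated sites. For the latter, use only scans taken before the lesion in question is irradiated, since section 11.1.11 allows later SRS or whole-brain treatment.
- Count patients who die or have no evaluable scan in the denominator as non-responders, and state whether a response needs confirmation.
- Keep week 12 and 1 year as supporting landmark rates, with one stated scan window for week 12.

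The cost is wording: the 3-monthly scans and their RECIST capture are already planned. The drawback is that best overall response is a more favourable figure than a landmark. It also depends on scan adherence and on how long imaging continues. Sections 10.2 and 13.1.2.4.1 move patients to telephone follow-up after progression, whereas section 13.1.2.3 continues 12-weekly imaging, and these should be reconciled. Showing best overall response beside the landmark rates lets readers judge this.

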#### **14.3.3 Overall Survival**

For overall survival, death from any cause will be defined as the event. Patients will be censored at time of last follow-up. OS will be estimated using the Kaplan-Meier product-limit method.

#### **14.3.4 Intracranial Outcomes**

Local control (LC), anywhere intra-cranial failure (also called distant brain failure, DBR), leptomeningeal disease (LMD), radionecrosis (RN) and symptomatic (SRN) – will be estimated using cumulative incidence methodology, with death considered a competing risk. Rates for these outcomes will be censored at the time of salvage whole brain radiation and/or last follow-up.

### **14.3.5 Biological variables**

**Descriptive statistics for the frequency and absolute cell counts for the major lymphocyte populations (CD3, CD4, CD8, CD19) T cells and monocytes (CD14) along with other markers listed above will be estimated.**

## **15.0 LABELING, PACKAGING, STORAGE AND RETURN OF CLINICAL SUPPLIES**

### **15.1 Investigational Product**

The investigator shall take responsibility for and shall take all steps to maintain appropriate records and ensure appropriate supply, storage, handling, distribution and usage of investigational product in accordance with the protocol and any applicable laws and regulations.

Clinical Supplies will be provided by Merck as summarized in Table 7.

Table 7 Product Descriptions

Product Name & Potency	Dosage Form
Pembrolizumab 50 mg	Lyophilized Powder for Injection
Pembrolizumab 100 mg/ 4mL	Solution for Injection

### **15.2 Packaging and Labeling Information**

Clinical supplies will be affixed with a clinical label in accordance with regulatory requirements.

### **15.3 Clinical Supplies Disclosure**

This trial is open-label; therefore, the subject, the trial site personnel, the Sponsor and/or designee are not blinded to treatment. Drug identity (name, strength) is included in the label text; random code/disclosure envelopes or lists are not provided.

### **15.4 Storage and Handling Requirements**

Clinical supplies must be stored in a secure, limited-access location under the storage conditions specified on the label.

Receipt and dispensing of trial medication must be recorded by an authorized person at the trial site.

Clinical supplies may not be used for any purpose other than that stated in the protocol.

### **15.5 Returns and Reconciliation**

The investigator is responsible for keeping accurate records of the clinical supplies received from Merck or designee, the amount dispensed to and returned by the subjects and the amount remaining at the conclusion of the trial.

Upon completion or termination of the study, all unused and/or partially used investigational product will be destroyed at the site per institutional policy. It is the Investigator's responsibility to arrange for disposal of all empty containers, provided that procedures for proper disposal have been established according to applicable federal, state, local and institutional guidelines and procedures, and provided that appropriate records of disposal are kept.

### **16.0 DATA AND SAFETY MONITORING PLAN**

The Data and Safety Monitoring Committee (DSMC) of the Winship Cancer Institute will provide oversight for the conduct of this study. The DSMC functions independently within Winship Cancer Institute to conduct internal monitoring functions to ensure that research being conducted by Winship Cancer Institute Investigators produces high-quality scientific data in a manner consistent with good clinical practice (GCP) and appropriate regulations that govern clinical research. Depending on the risk level of the protocol, the DSMC review may occur every 6 months or annually. For studies deemed High Risk, initial study monitoring will occur within 6 months from the date of the first subject accrued, with 2 of the first 5 subjects being reviewed. For studies deemed Moderate Risk, initial study monitoring will occur within 1 year from the date of the first subject accrued, with 2 of the first 5 subjects being reviewed. Subsequent monitoring will occur in routine intervals per the [Winship Data and Safety Monitoring Plan \(DSMP\)](#).

The DSMC will review pertinent aspects of the study to assess subject safety, compliance with the protocol, data collection, and risk-benefit ratio. Specifically, the Winship Cancer Institute Internal Monitors assigned to the DSMC may verify informed consent, eligibility, data entry, accuracy and availability of source documents, AEs/SAEs, and essential regulatory documents. Following the monitoring review, monitors will provide a preliminary report of monitoring findings to the PI and other pertinent individuals involved in the conduct of the study. The PI is required to address and respond to all the deficiencies noted in the preliminary report. Prior to the completion of the final summary report, monitors will discuss the preliminary report responses with the PI and other team members (when appropriate). A final monitoring summary report will then be prepared by the monitor. Final DSMC review will include the final monitoring summary report with corresponding PI response, submitted CAPA (when applicable), PI Summary statement, and available aggregate toxicity and safety data.

The DSMC will render a recommendation and rating based on the overall trial conduct. The PI is responsible for ensuring that instances of egregious data insufficiencies are reported to the IRB. Continuing Review submissions will include the DSMC recommendation letter. Should any revisions be made to the protocol-specific monitoring plan after initial DSMC approval, the PI will be responsible for notifying the DSMC of such changes. The Committee reserves the right to conduct additional audits if necessary.

**Product:** Pembrolizumab (MK-3475)

67

**Protocol/Amendment No.:** Rad3179-16 (MK-3475-423), v.6/23/17

### 16.1. **Data Collection:**

Data that will be captured in OnCore for the following procedures

- Inclusion/Exclusion Criteria
- Demographics and Medical History
- Vital Signs
- Weight
- Karnofsky Performance Status (KPS) & ECOG
- HBcAb, HepC Ab
- Brain MRI [RECIST]
- Diagnostic Imaging [RECIST]
- Adverse Events Assessment
- CBC with differential
- CMP, LDH, ESR
- T3, FT4, TSH
- Pregnancy Test – urine or serum b-HCG
- Urinalysis
- Uric Acid, MG, Phos, Coags (PTT, PT, INR) - [seconds]
- Serum Biomarkers
- Skin Biopsy (if needed)
- Stereotactic Radiosurgery
- Survival Analysis
- Grade 3 CNS

**Product:** Pembrolizumab (MK-3475)  
**Protocol/Amendment No.:** Rad3179-16 (MK-3475-423), v.6/23/17

68

## **17.0 APPENDICES**

### **APPENDIX I**

#### **CTCAE (Common Terminology Criteria for Adverse Events), version 4.03**

The exact full criteria for toxicity assessment can be obtained at the NCI CTEP website at the following link:

[http://evs.nci.nih.gov/ftp1/CTCAE/CTCAE\\_4.03\\_2010-06-14\\_QuickReference\\_8.5x11.pdf](http://evs.nci.nih.gov/ftp1/CTCAE/CTCAE_4.03_2010-06-14_QuickReference_8.5x11.pdf)

## **APPENDIX II**

### **Tumor assessment via RECIST Criteria, Guideline Version 1.1**

<http://imaging.cancer.gov/clinicaltrials/imaging>

### **APPENDIX III**

#### Tumor Assessment per Immune-Related Response Criteria

Immune-related Response Criteria (irRC) are derived from modified World Health Organization (mWHO) conventions. Assessments of lymph nodes are derived from current RECIST guidelines.

#### **a.) Definitions of Measurable/non-Measurable Lesions**

All measurable and non-measurable lesions should be assessed at the initial Screening/enrollment, at the defined tumor assessment time points (see Time and Events Schedule), and during regular maintenance. Additional assessments may be performed, as clinically indicated for suspicion of progression. The Investigator will base response to treatment using the irRC.

##### **i.) Measurable Disease**

Measurable non-lymph node disease is defined as lesions that can be accurately measured in 2 perpendicular Diameters. Size criteria is defined based on the properties of the CT scan

-Spiral CT, 0.5cm thickness slice: both diameters must be at least  $\geq 1.0$ cm

-For  $> 0.5$ cm thickness slices: larger diameter  $>2.0$ cm; the other  $> 1.0$ cm

Lymph nodes are measurable only if CT slice thickness is  $<0.5$ cm. Size criteria are that the lymph node be at least 15 mm in short axis.

